5.1 Common issues

Two interventions will be allocated to respondents – the provision of information on CVD risk and the offer of a lottery ticket conditional on going for a checkup. The study is a randomized parallel experiment with two separate, non-overlapping treatment groups and one control group. Randomization will be done at the level of the barangay, which is the smallest administrative unit in the Philippines roughly equivalent to an electoral ward.

Soliciting the participation of the LGUs. After the sample barangays have been drawn and assigned to the treatment arms, the study team will schedule visits with the corresponding local chief executives (LCE) and the municipal/city health officer (MHO/CHO) to solicit their participation. A standard letter will be delivered stating the aims of the study and clarifying that several barangays in a municipality will be assigned to different treatment arms. An agreement will be drafted stating the responsibilities of UPecon Foundation R4D Study Team and the Local Government Units (LGUs). The terms of the agreement will explicitly state which barangays will be included in the study and in which barangays sampled residents will be given the lottery tickets on condition of attendance at the RHU/CHC. We will explore whether the budget will allow giving a small token of appreciation to the LCE and the MHO after the follow-up survey is completed, signalling the end of the field work part of the study.

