Voucher contents. The voucher will indicate "This voucher entitles ______ (to be filled in) to a ticket for a lottery offering a 1 in X chance of winning Php 5000." To make the voucher credible, it will carry the name, signature and contact details of the local study team head. It may also carry an endorsement of the Mayor or the MHO, evidenced by their signature or stamp. The voucher will also indicate the claiming period, the facility where the ticket can be claimed and the name of the point person in that facility, i.e., "To claim your ticket, you must see Ms/[name] at xxx Health Center for a physical assessment before XXXX. The lottery will be drawn on XXX"

⁵ The minimum daily wage in Region III, where Nueva Ecija is located, is P334, P364 and P353 in the agricultural, non-agricultural and service sectors respectively in 2017.

Ticket contents. The ticket will contain the same information as the voucher: number, study team leader, endorsement of LCE or MHO. In addition, the ticket will contain the date when the prize will be drawn (respondents will be given one month to claim the lottery tickets and will be advised of the date of the draw, which is one week after the claiming period) and the number that can be called to confirm whether the respondent has won, or to obtain any other information.

Informing the RHU/CHC of potential lottery ticket recipients. Upon the completion of each day's interviewing, the enumerator will provide the list of interviewed voucher recipients (with their names, addresses, and voucher numbers) to the RHU/ CHC facility point person via SMS or email with a copy to the UPecon team.

Survey operations. The UPecon team will give pre-numbered vouchers to the survey enumerators. The survey team would have to record the names of the sampled respondents given the vouchers and report the same to the UPecon team by SMS or email when the interview is finished. The survey team should also inform the RHU/CHC point person by SMS or email the recipient of the voucher as well as the voucher number. Unused vouchers will be surrendered to the UPecon team at the end of the baseline survey.

Interview procedure.

- a. *Before the interview*. In barangays where the lottery treatment will be implemented, the informed consent form will include a line that requests the respondent to agree to having their name, contact number sent to the RHU/CHC. The consent form will indicate that these are for the purpose of verifying identity at the RHU/CHC.

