The primary sampling unit (PSU) and the level at which treatment will be randomly allocated is the barangay. The is the lowest administrative unit in the Philippines. There are 849 barangays in Nueva Ecija. Barangays will be randomly drawn for inclusion in the study and randomly allocated to one of the two treatment groups or the control group with probabilities set to achieve the required sizes of the groups.

Within a barangay, interval sampling will be used: starting from a random location, a procedure will be followed to randomly select households moving out from that point. Selected households will be screened to establish whether each includes anyone aged from 40 to 70 inclusive. If so, one such person will be randomly selected as the main survey respondent and the potential subject of the intervention in the treatment group barangays. Further screening will be undertaken to establish whether the selected person is eligible for the study, mainly on the basis of CVD history (see next section). In addition to the main respondent, we will ask the head of household, spouse or other adult to answer questions about the household in general.

9. Inclusion and exclusion criteria

We restrict attention to individuals aged 40 and above because this is one of the criteria for proceeding from risk assessment to risk screening under the PhilPEN protocol. Hence, we know that all respondents

induced to go for a checkup should be given a full screen with tests for blood glucose, urine protein and, if available, blood lipids. By restricting attention to the 40+ age group, we focus on the population in which CVD risks begin to rise steeply and preventive care is most needed. In addition, Globorisk predicts 10-year CVD risk only for individuals aged 40-74. We exclude those older than 70 because comorbidities are likely to rise steeply beyond that age, and because older individuals are likely to be more cognitively challenged in responding to the risk perceptions and risk attitudes questions.

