Individuals who report a diagnosis of heart disease, heart attack, stroke or diabetes, or who are taking medication for hypertension or diabetes will be ineligible. We must first screen the initially sampled individuals to identify these cases. Using data from the NNS, we estimate this group will amount to 14% of those initially sampled. Other sampled individuals will be eligible but will refuse to give consent to participate. We assume 15% of those sampled will not give their consent. Costs will be incurred performing the initial screening of sampled households before the ineligible and non-consenting cases are identified. We adjust the initially selected sample upwards to allow for these non-usable respondents. A similar adjustment is made for an assumed 5% of the eligible sample who will not answer all requisite questions or complete all measurements despite initially giving consent.

Compliance rate

Not all respondents who are offered a voucher will go to a RHU/CHC for a checkup and so get the lottery ticket to which they are entitled. And some of the control group will go to the RHU/CHC despite not being offered any inducement. We have no firm evidence on which to hazard a guess about the extent to which the offer of a lottery ticket will be effective in persuading people to go for a checkup. Based on the facts that the offered prize of P5000 (US\$100) is roughly equivalent to 14 days' earnings at the average wage in the province, and from discussions with health workers in the area, we believe that response will be high. We assume a compliance rate of 60% and conduct sensitivity analysis setting this as low as 50%.

Table 4 summarises all the parameter values used in the various scenarios considered in the power calculations.

Parameters	Scenario 1 (main)	Scenario 2	Scenario 3	Scenario 4	Scenario 5
Significance level (α)	0.05	0.05	0.05	0.05	0.05
Power $(1-\beta)$	0.8	0.8	0.8	0.8	0.8
Minimum detectable	0.2	0.2	0.2	0.2	0.2
standardized effect size (δ)					
Attrition rate	0.1	0.1	0.1	0.1	0.1
Refusal to consent rate	0.15	0.15	0.15	0.15	0.15
Item non-response rate	0.05	0.05	0.05	0.05	0.05
Ineligibility rate	0.14	0.14	0.14	0.14	0.14
Average cluster size at follow-up	10	10	10	10	10
Intra-cluster correlation	0.1	0.05	0.1	0.05	0.1

Table 4 Parameter values used in power calculations

Autocorrelation in outcomes	0.6	0.6	0.6	0.6	0.4	
Compliance rate in lottery intervention	0.6	0.6	0.5	0.5	0.6	

	Control group	Treatment group	
Mean CVD risk	11.35	10.89	

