- Voluntary nature of the survey and right of respondent to stop the interview at any time.
- That follow-up survey to be conducted after 6-7 months.
- That confidentiality of the information shared and the identity of the respondent will be protected.
- That the respondent may ask for clarifications to the enumerator; or call study team members through the contact numbers or email provided for any complaint, question or clarification.
- That the respondent indicates consent by writing his/her name, signing over it and specifying the date in front of the enumerator.

The text of the consent form will be read by the enumerator before proceeding with the interview. Only when the consent form is signed by the respondent and the "consent and sign" option is ticked will the interview proceed.

Respondents in the lottery treatment group will be asked to sign an additional consent form to confirm their acceptance of the conditions under which the lottery will be conducted and they will be allowed to enter it. This includes information on what they must do to collect a lottery ticket from a RHU/CHC, which facility they must attend, by what date and how the winners will be informed (see Appendix D).

There is no separate consent form to confirm participation in the information treatment. This intervention does not involve the provision of any medical care, nor the offer of a financial reward on condition of seeking preventive care. Respondents are simply informed of the risk of heart attack/stroke within 10 years conditional on age, sex, blood pressure, BMI and smoking status. Respondents are told that these risks are estimated by doctors based on monitoring the health of thousands of individuals over many years. They are told that the estimates are specific to the Philippines.

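### Only lottery barangays see an extra data-sharing request on the consent form signed before the baseline interview, so who consents could differ between the lottery and control arms

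*Combined protocol and SAP*

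**What the plan says.** Section 8 (Sampling) sets the unit of allocation: "The primary sampling unit (PSU) and the level at which treatment will be randomly allocated is the barangay". Section 5.1 places visits to local officials "After the sample barangays have been drawn and assigned to the treatment arms", so the arm of a barangay is fixed before any resident is approached.

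Section 12 (Consent Process) makes consent the gate to the baseline sample: the interview goes ahead "Only when the consent form is signed by the respondent" and the matching option is ticked.

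Section 5.3, under the interview procedure, step (a), adds the arm-specific element. In lottery barangays only, "the informed consent form will include a line that requests the respondent to agree to having their name, contact number sent to the RHU/CHC". The stated purpose is to verify identity there. The list of consent contents in section 12 does not mention this line.

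Step (b) of section 5.3 comes after the interview. The lottery is explained, and the respondent signs a form on its terms. Section 12 describes what appears to be the same form: "Respondents in the lottery treatment group will be asked to sign an additional consent form to confirm their acceptance of the conditions". The details sent to the facility, at the end of each day's interviewing, are those of voucher recipients only.

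Section 10.1 uses a single refusal figure for all arms: "We assume 15% of those sampled will not give their consent". Neither a comparison of consent by arm nor an analysis for differential consent is planned.

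**The concern.** In a cluster trial, randomisation makes the residents approached comparable across arms. Comparability of the people enrolled also requires that recruitment after allocation works the same way in each arm. Here the lottery arm is asked something before enrolment that the other two arms are not.

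The request concerns the facility whose attendance is the exposure in equations 6.1 and 6.2. People wary of being known to the RHU/CHC may attend less, and their risk factors may change differently over the following months. If some of them refuse in lottery barangays but join in control barangays, the lottery-control comparison no longer rests on randomisation alone. That comparison carries the evaluation of PhilPEN, and it is powered for a deliberately small effect, so a modest bias could matter. A larger sample would not remove it.

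The early timing also looks unnecessary, because no name is sent until a voucher has been given at the end of the interview.

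**Working it through.** **Order of events.** Barangay assigned (5.1, 8); respondent selected and screened (8, 9); consent form signed, with the extra line in lottery barangays only (5.3 step a, 12); baseline interview; lottery explained, voucher given and lottery form signed (5.3 step b, 12); names sent to the facility that day (5.3). The request comes after allocation and before entry to the sample, but well before it is needed.

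**The plan's own figure.** Inputs from section 10.1: two-sided 5% (sidedness assumed), 80% power, effect 0.2 SD, compliance 0.6, ICC 0.1, 10 per cluster at follow-up, baseline correlation 0.6.

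- Effect of the offer: 0.2 × 0.6 = 0.12 SD.
- n per arm = 2 × (1.96 + 0.84)² / 0.12² × (1 − 0.6²) × (1 + 9 × 0.1) ≈ 1,326, against 1,306 in Table 6 for mean CVD risk.
- With the rounded means in Table 5 (11.35 and 10.89; SD 11.35/5 = 2.27), about 465 per arm is needed at full compliance. That is 47 clusters of 10, or 470, and 470/0.36 = 1,306.

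The figure reproduces, and this point disputes no number in the plan. At the adopted size of 1,361 per arm, the standard error of the offer effect is √(2/1,361 × 1.9 × 0.64) = 0.042 SD.

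**Bias.** Let q be the share of would-be consenters lost because of the line. Let D be the gap in follow-up outcome between those lost and those kept, in SD, that the baseline outcome and covariates do not explain. Then:

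- bias in the offer effect (ITT) = q × D;
- bias in the instrumental-variable (IV) estimate = q × D / 0.6, holding compliance at 60%.

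The documents give neither q nor D. Assume refusal of 15% in control and 20% in lottery barangays: q = 0.05/0.85 = 5.9%. Type I error of the ITT test is Φ(−1.96 + bias/SE) + Φ(−1.96 − bias/SE).

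| D (SD) | ITT bias (SD) | IV bias (SD) | IV bias as % of 0.2 SD | Type I error |
|---|---|---|---|---|
| 0.05 | 0.003 | 0.005 | 2.5% | 5.1% |
| 0.1 | 0.006 | 0.010 | 4.9% | 5.2% |
| 0.2 | 0.012 | 0.020 | 9.8% | 5.9% |
| 0.5 | 0.029 | 0.049 | 24.5% | 10.7% |

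Ten extra points of refusal instead of five would double each bias.

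**Losing only people who would not attend.** Suppose those lost would not attend even with the offer, and their untreated outcomes match those of the people kept. With no attendance in control, lottery attendance among those kept is 0.6 × 0.85/0.80 = 0.6375. The offer effect becomes 0.2 × 0.6375 = 0.1275 SD, and the IV ratio is 0.1275/0.6375 = 0.2 SD, unchanged. Loss of this kind inflates the first stage but leaves the IV estimate intact.

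**Power.** At 20% lottery refusal the lottery arm falls to 1,361 × 0.80/0.85 = 1,281, and power for 0.12 SD goes from 81.0% to 79.8%. The issue is bias, not power.

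**The case against.** The strongest reply is that the mechanism depends on a form whose wording I could not read. The Appendix D forms are not in the public text, and section 5.3 says only that agreement is requested. A reader might infer that declining the line bars a person from the study. The documents do not say so, and if the line is a separate opt-in the selection is weaker.

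A reader might also infer that the line reveals the arm before enrolment. It does show that the RHU/CHC is involved, but the purpose given is identity verification. The prize and the chance of winning are explained only after the interview. Enumerators in lottery barangays carry the vouchers and know the arm whatever the form says.

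On size, it would be tempting to put the raw difference between refusers and consenters into the formula. The planned model conditions on the baseline outcome and many covariates (sections 3.2 and 10.1). The principal outcome is computed from age, sex, smoking, BMI and blood pressure, all recorded at baseline. Only a difference in unexplained change over 6 to 7 months counts. At the plan's SD of 2.27, D = 0.5 is 1.14 risk points, more than the 0.2 SD (0.45 points) sought from a checkup itself. The upper rows of the table are therefore demanding.

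Finally, telling people at the outset that a third party will receive their details is a defensible transparency choice.

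All of this limits the size and certainty of the problem. None of it removes the arm-specific step before enrolment, and baseline adjustment is not guaranteed to capture reluctance to deal with the facility.

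**Conclusion.** The concern holds as a possible, unquantified recruitment bias in the lottery-control comparison, for both the offer effect and the IV estimate. On the assumed 20% against 15% refusal and residual differences of 0.05 to 0.5 SD, the bias is about 0.003 to 0.03 SD (ITT) and 0.005 to 0.05 SD (IV), or 2.5% to 25% of the 0.2 SD target. It is smaller if declining the line does not exclude a person, or if those lost are mainly people who would not attend. The direction cannot be told from the documents. They do not support a claim that the estimate is biased, only that the design leaves avoidable room for it and plans no check.

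**What to change.** - Use identical pre-baseline consent text in all three arms.
- Move the request to share name and contact number to the additional lottery form signed after the interview, so that permission is still obtained before any name is sent.
- Analyse everyone enrolled in lottery barangays as offered, whether or not they agree to sharing.
- Report the numbers approached, eligible and consenting by arm.

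If the line must stay on the first form, state whether declining it excludes a person.

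The cost is rewording two forms, with no change in sample size. There is one downside. Under the instructions to the facility point person, a voucher holder who is not on the list gets no ticket. Anyone who declines sharing could not take up the offer unless identity is verified another way, which may slightly lower compliance below the assumed 60%.
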